## **Risks and Benefits**

Participants risk loss of confidentiality. Participants might feel uncomfortable disclosing personal information, might become bored during the research sessions, or might become frustrated with the tasks. Alcohol-dependent adults that reduce alcohol drinking might experience mild alcohol withdrawal (e.g., anxiety, agitation, headache, hypertension, insomnia, irritability). There are no other foreseeable risks for participants.

The study will be conducted at the Virginia Tech Carilion Research Institute.

Participants will be screened, using medical history and structured interviews, for a history of medical contraindications (e.g., pregnancy), current unstable medical illness and psychiatric disorders. Participants will be free to withdraw from the study at any time, and their refusal to continue will not affect other medical care associated with Carilion Clinic. In addition, if participants develop medical problems during the course of the study, assessments to determine whether participants should continue will be conducted and necessary referrals will be provided. Using only ID numbers and keeping all data in limited-access areas in locked offices will protect confidentiality. Computer databases will have coded identifiers, and all study team members will be trained in the protection of human subjects. These screening, monitoring, and confidentiality

procedures have been in effect for more than 10 years and for more than 1,000 subjects across the various protocols employed by our group across various institutions.

Participants will also be educated about the risks of alcohol withdrawal and will be provided with contact information for emergency medical care in the event that they experience alcohol withdrawal symptoms that warrant medical care. No other foreseeable risks exist for participants.

Participants may benefit from possible reduction in alcohol use or cessation of alcohol use. The project involves minimal risk to confidentiality or other personal rights or to physical or emotional health. Thus, the expected benefits outweigh the very minimal risks to participants.

## **Data Protection**

All data, including any identifiable information, and participant binders will be stored in a safe place to protect confidential participant information. Safe places will include locked filing cabinets or locked rooms accessible only to study personnel. The full names of participants will not be listed on the outside of binders to protect confidentiality of study participants.

Electronic data will be saved in secure, limited access shared drives on password-protected computers accessible only to the research team. Breathalyzer data will also be stored on secure SOBERLINK servers located within the United States during the

period of active data collection for this study only, after which point it will be completely deleted.

## **Participant Compensation**

Participants will receive

- \$15 compensation for the consent session
- \$15 for completion of assessment measures
- up to \$7 compensation for completion of the daily self-reports during the baseline period
- \$15 for completion of the pre-intervention (second) session
- 15 for the third session
- \$30 for the last follow-up assessment session
- up to \$56 for submission of the breathalyzer assessments and reports of previous-day drinking for the 14-day intervention
- \$50 for returning your SOBERLINK device and prepaid cell phone (if applicable)

These payments will be up to \$203 per participant, but may be less (depending on what study procedures he/she has completed).

To allow for payments that are both convenient and rapidly available, we will pay participants with reloadable prepaid cards through Greenphire ClinCard ([www.greenphire.com](http://www.greenphire.com)), an FDIC-insured payment provider that specializes in clinical trial stipend payments that comply with IRB privacy regulations and considerations. At

intake, each participant will receive a prepaid MasterCard debit card that can be used anywhere that accepts MasterCard. As payments are earned in the course of the study, additional funds will be added to the account for that participant. Funds are immediately available when added and participants can check their balance as desired. This system will allow frequent, immediately available payments without the burden of frequent laboratory visits that would negate some of the advantages of remote alcohol monitoring.

RMET15-955 Episodic Thinking (ET) as a Candidate Technique to Reduce
Alcohol Consumption

Statistical Analysis Plan

10/26/2017

Statistical Analysis Plan

Descriptive statistics, chi-square, and t-test will be used to compare means and frequencies of sample characteristics among the two groups. Paired t-tests will be carried out to compare alcohol consumption, rates of discounting, alcohol valuation, PANAS measures, and craving scores before and after the intervention within groups. Discounting of delayed money will be assessed using an adjusting-delay task (Koffarnus and Bickel 2014) and an adjusting-amount task (see Du, Green, and Myerson 2002). Discount rate in both tasks will be calculated using the following hyperbolic equation, (Mazur 1987)

$$V = \frac{A}{1 + kD}$$

In this formula, V refers to the discounted value of a delayed reward; A represents the amount of the delayed reward; D equals the delay of the award; and k represents the delay-discounting rate (Mazur 1987). A higher k value means steeper discounting curve and reflects greater impulsivity, while lower k value means shallower discounting curve with less impulsivity. To provide an estimate of k , we will fit the hyperbolic equation to participants' indifference points (given in discounted monetary value), and use its natural log transformation in analyses. All the statistical analyses will be conducted using Prism 7 at a significance level of 0.05.

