### **Participants**

Up to 200 alcohol-dependent adults will enroll in this study. Participants must

- (1) provide written informed consent,
- (2) be 18-65 years old,
- (3) meet DSM-V criteria for moderate or severe alcohol use disorder, and
- (4) express a desire to quit or cut down on their drinking.

Individuals who are pregnant or lactating (through urine screen at time of consent), meet DSM-V criteria for any other moderate or severe substance use disorders (excluding caffeine, nicotine, and marijuana), score 23 or greater on the Alcohol Withdrawal Symptom Checklist (a score indicating that medication would be likely required to manage alcohol detoxification, see Pittman et al., 2007), use prescribed or over-the-counter medicines containing alcohol, participated in any previous studies that included EFT and conducted at the Addiction Recovery Research Center in the last 3 months, or have immediate plans to move out of the area will be excluded from participation. Participants may be compensated based on time and travel.

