## **Procedures**

Study design. After the initial consent and assessment sessions, participants will be asked to provide daily self-report assessments of previous-day drinking over cell phone (see below) for 7 days with no other study intervention taking place. The purpose for this baseline period is to quantify baseline drinking patterns and ensure that the participant reliably responds to and conveys study information via cell phone. At the end

of this baseline period, participants who indicated adequate patterns of drinking and successfully reported their level of drinking as requested on baseline days will be invited to continue in the study. Participants will return to the laboratory to be provided with a SOBERLINK breathalyzer and be given instruction in its use.

Participants will be counterbalanced to either the active or control group based on alcohol use (e.g., average drinks per day). Both groups will be exposed to the same treatment events. The intervention period will last for 14 consecutive days, with three breathalyzer screens per day. During this 14-day period as they did during the baseline period, participants will self-report their previous-day alcohol use daily with a text message and/or phone call. Assessment sessions will be conducted prior to the intervention, immediately following the intervention, and at a 1-month follow-up.

Participants will be provided with a prepaid cell phone (if necessary) at the beginning of the study and a SOBERLINK breathalyzer at the beginning of the 14-day period, and receive a \$50 study completion bonus at the end of the study provided these devices are returned.

Cellular phone communication. All participants will either be allowed to use their own personal cell phone for study communications or receive a prepaid cell phone with service through a nationwide cell phone service provider that specializes in providing powerful usage controls with their cell phones, allowing us to restrict phone communication to a study phone and 911 service. If a participant chooses to use his or her personal cell phone for study communications and pays for text messages and/or phone calls on a per unit basis, we may reimburse the participant for the cost of those

messages and calls made for this study. We have used study-provided cell phones to facilitate study communication previously (Koffarnus et al., 2011).

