Daily alcohol use self-reports. Each day, participants will be asked to report how many alcoholic drinks they consumed the previous day (from the time they awoke to the time they fell asleep). We will ask them about the previous day alcohol use instead of the current day to best capture all drinks consumed each day without inconsistent response times complicating the measurement. Participants will be allowed to report this information at any time throughout the day, but will be encouraged through prompts to do so in the morning to increase the likelihood of accurate recall of previous day use. Participants will be allowed to report this information via text message or phone call. Participants will receive a reminder to report their previous-day drinking with text messages, followed by a phone call if they haven't contacted us by early evening. For completing this daily self-report, participants will receive \$1 in compensation.

Assessment sessions. Assessment sessions will be completed before the 14-day intervention period, immediately after the 14-day intervention period, and at a 1-month follow-up. Participants will complete a battery of questionnaires and tasks grouped into

three general categories: measures of substance use (including a urine test for drug and alcohol metabolites and a breath sample to test for recent alcohol use), clinically relevant measures including treatment acceptability, and measures of alcohol value and sensitivity.

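### Paired t-tests on an undefined 'after' value handle drinking-related withdrawal badly; a mixed model on the daily reports would use the data already collected

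*SAP*

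**What the plan says.** The SAP's only test of drinking is in one sentence: "Paired t-tests will be carried out to compare alcohol consumption", along with discounting, alcohol valuation, PANAS and craving, before against after and within groups. Between-group tests are mentioned only for sample characteristics. The SAP does not define the before and after values, and it gives no analysis population, missing-data rule or sensitivity analysis. It adds that "All the statistical analyses will be conducted using Prism 7 at a significance level of 0.05".

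The protocol (Procedures) collects much more than two values per person. The baseline phase consists of "daily self-report assessments of previous-day drinking over cell phone (see below) for 7 days", and only people who report as asked are invited to continue. During the 14 intervention days, "participants will self-report their previous-day alcohol use daily with a text message and/or phone call". The quantity is a drink count: "Each day, participants will be asked to report how many alcoholic drinks they consumed the previous day". Under Risks and Benefits, "Participants will be free to withdraw from the study at any time".

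The Introduction states the hypothesis as a reduction over the two weeks under EFT compared with control.

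**The concern.** A paired t-test needs one before and one after value per person, so up to 21 daily reports (7 + 14) must be reduced to two numbers. The SAP leaves open how. 'After' could be a complete 14-day mean, a value from the post-intervention session, or the mean of whichever intervention days were reported.

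The choice matters because the outcome is itself a plausible reason for leaving. Someone drinking more than usual may stop reporting.

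- If such people are dropped, those who remain look better than the group assigned.
- If they are kept with a short mean, that mean often ends on a run of heavy days. It then counts as much as a 14-day mean.

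The first error makes drinking appear to fall, the second to rise. The SAP plans no between-group test of drinking, so nothing in the planned analysis would cancel a bias shared by both arms.

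**Working it through.** **Inputs from the documents.** 7 baseline and 14 intervention daily reports; significance level 0.05; enrolment capped at 200. There is no dropout rate, SD, effect size or power figure, so there is no planned figure to reproduce.

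**Assumed inputs (simulation A).** 75 per arm; mean 6 drinks/day; between-person SD 3; day-to-day SD 4; SD of personal change 2; zero true change. The hazard of leaving rises 28% per drink by which the 3-day running mean exceeds the person's own baseline.

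| Analysis, about 18% dropout | Estimated change (truth 0) | Rejection rate (nominal 5%) |
|---|---|---|
| Paired t-test, completers only | about −0.35 | about 18% |
| Paired t-test, available-day means | about +0.15 | about 7% |
| Mixed model on daily reports | about +0.01 | about 5% |

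At about 10% dropout the completers-only figure is −0.20. Available-day means give +0.06 to +0.09, with rejection near 5%.

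**Hand check of the rejection rates.** The SD of a person's observed change is √(2² + 4²/7 + 4²/14) = √(4 + 2.29 + 1.14) = 2.73.

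- Completers: n = 75 × 0.82 = 61.5, so SE = 2.73/√61.5 = 0.35. The shift is 0.35/0.35 = 1.0 SE, and P(Z > 0.96) + P(Z < −2.96) ≈ 0.17.
- Available days: SE ≈ 2.73/√75 = 0.315. The shift is 0.15/0.315 = 0.48 SE, and P(Z > 1.48) + P(Z < −2.44) ≈ 0.08.

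Both agree with the simulation.

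**Analytic check of the completers' bias.** Let d be the dropout share and r the correlation between the tendency to leave and the change in drinking. Under normal selection the bias is −r·φ(z₁₋d)/(1 − d), in SDs of the change. For d = 0.20 and r = 0.5: −0.5 × 0.280/0.80 = −0.175. Across d = 10%, 20%, 30% at r = 0.5 it is −0.10, −0.18, −0.25. At r = 0 it is zero. The simulated 0.35 is 0.35/2.73 = 0.13 SD, so only a moderate r is needed.

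**Different assumptions (simulation B).** 100 in one arm, SDs 3 (between-person), 3 (day-to-day) and 2 (change), withdrawal possible from day 4, 200 replicates, simulation error about 0.02.

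| Reason for leaving | Dropout | True change | Completers | Available days | Mixed model |
|---|---|---|---|---|---|
| Random | 21% | 0 | +0.01 | +0.01 | +0.01 |
| Baseline level only | 19% | 0 | +0.08 | +0.01 | +0.01 |
| Reported drinking above baseline, moderate | 19% | 0 | −0.33 | +0.07 | +0.03 |
| Same, strong | 19% | 0 | −0.55 | +0.07 | 0.00 |
| Reported drinking above baseline, moderate | 16% | −1 | −1.28 | −0.96 | −1.00 |
| Unreported day's drinking | 15% | 0 | −0.21 | −0.03 | −0.05 |

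**Why the mixed model does better.** It uses the reported days that led up to the withdrawal and weights each person by information. With day-to-day SD 4, a 3-day mean has within-person variance 16/3 = 5.3, against 16/14 = 1.1 for 14 days. The paired test treats the two alike. The available-day rise is larger when people can leave very early, because the shortest series then carry full weight.

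**Imputing the baseline mean.** In simulation A, setting missing intervention days to the person's own baseline mean gave about −0.13 with no true change. People who leave while drinking above baseline are then credited with a return to baseline.

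**The case against.** The strongest objection is that the SAP does not specify a completers-only test. If 'after' is the mean of the days reported, someone who leaves midway stays in, and the error is less than half as large. The protocol also works to keep people reporting: a run-in that admits only reliable reporters, a payment for each report, and reminders with a follow-up call. Dropout may be low, and if it is unrelated to changes in drinking there is no bias.

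Most of this stands. A reader might infer that the plan deletes everyone who withdraws and therefore overstates the reduction. The documents do not support that, because 'after' is undefined and the sign of the bias depends on how it is read. A reader might also infer a biased EFT–ERT difference: in simulation A it was −0.35 drinks/day among completers when 20% dropout depended on drinking in the EFT arm only. But the SAP plans no between-group test of drinking, and nothing in the documents points to dropout that differs by arm in this way.

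The objection does not rescue the method. Nothing in the SAP selects the available-day reading. That reading is still biased when withdrawal follows reported drinking, and it still loses anyone with no intervention report. Payments and reminders make loss less likely but do not say how to analyse those who leave.

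Two limits apply to the remedy. It was tested on normally distributed data, whereas real drink counts may be skewed. It also relies on missing-at-random.

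**Conclusion.** The point holds in conditional form. If withdrawal depends on reported drinking relative to the person's own baseline, the paired t-test is biased under either reading of 'after': about −0.35 drinks/day for completers and about +0.15 for available-day means, at about 18% dropout with no true change. The mixed model stays within about 0.03 of the truth in these scenarios, and within about 0.05 when withdrawal depends on unreported drinking.

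Every dropout rate, SD and withdrawal mechanism here is assumed. The direction of bias in this trial cannot be known from the documents, and random withdrawal would produce none. The argument covers alcohol consumption only, because no daily series is described for discounting, valuation, PANAS or craving. The change is worth making: the better analysis uses data already being collected and answers the Introduction's question, which a within-group test does not.

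**What to change.** Replace the paired t-test for alcohol consumption with SAP text to this effect:

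- **Data and population.** All daily drink reports from the 7 baseline and 14 intervention days, for everyone assigned to EFT or ERT, including those who withdraw.
- **Model.** Linear mixed model with fixed effects for period, group and period × group, and a person-level random intercept and random period effect. Report the period × group estimate with its confidence interval as the EFT–control result. Check residuals, since the counts may be skewed.
- **Sensitivity analysis.** A missing-not-at-random analysis that sets missing intervention days to the participant's own baseline mean plus a pre-stated range of increments starting at zero. Report where the conclusion changes. The baseline mean alone is not enough, because it still favours a reduction.
- **Other outcomes.** State separately the analysis population and missing-data rule for discounting, valuation, PANAS and craving, which the daily reports cannot help.

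The cost is SAP wording, some extra analysis, and a change to the sentence that ties all analyses to Prism 7 so that software fitting this model may be used. The main model relies on missing-at-random, and the sensitivity analysis shows how far the result depends on it. No new data or visits are needed.

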## **Study Protocol**

### **Introduction**

Nearly 18% of United States adults meet criteria for alcohol dependence sometime in their lifetime, with only 24% of those individuals ever receiving any treatment for their disorder (Hasin et al., 2007). The pervasiveness of alcohol dependence indicates a need for continued development of high-impact treatments that are both effective and easily disseminated to a broad population. Recent evidence indicates that Episodic Future Thinking (EFT), the ability to self-project and pre-experience a future event, can help individuals to make changes to habitual behaviors, such as alcohol drinking (Snider et al., 2016). Here, we will evaluate the efficacy of EFT to help individuals reduce alcohol consumption. We anticipate that EFT will result in a reduction in alcohol consumption over a 2-week experimental period when compared to the control group.

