## **Recruitment**

This project will use recruitment strategies and procedures that are successful in the recruitment and retention of the targeted samples at the Addiction Recovery Research Center. Specifically, participants will be recruited from the Roanoke and Blacksburg, VA communities using IRB-approved study advertisements via posted flyers, and the Internet (e.g., Craigslist, Facebook, etc). Advertisements will include descriptions of the studies and contact information.

To the extent possible, we will attempt to minimize obstacles to participation. For example, travel barriers will be addressed by providing transportation or parking costs to participants, and scheduling barriers will be minimized by offering a flexible assessment schedule. All methods and measurement will be conducted using standard operating procedures, and all staff (including recruitment staff) will be provided with cultural

sensitivity training. We have a history of successful recruitment of alcohol-dependent adults into research programs. All participants will enroll on a voluntary basis and sign an IRB-approved consent form prior to study participation.

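### The SAP tests drinking only before versus after within each group, so the protocol's EFT-versus-control hypothesis has no planned estimate, interval or test

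*SAP*

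**What the plan says.** The protocol states one hypothesis, in its Introduction: "EFT will result in a reduction in alcohol consumption over a 2-week experimental period when compared to the control group". That is a contrast between two groups.

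The SAP is a single section. Its first sentence plans descriptive statistics, chi-square and t-tests to "compare means and frequencies of sample characteristics among the two groups". Its second sentence plans paired t-tests on "alcohol consumption, rates of discounting, alcohol valuation, PANAS measures, and craving scores before and after the intervention within groups". The rest defines the discount rate and its log transformation, and names the software and the 0.05 level. The protocol has no statistics section. Neither document contains a two-sample comparison of outcome or change, an ANCOVA, a group-by-time term, a between-group effect measure or a confidence interval.

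**The concern.** A paired t-test within one arm tests whether mean drinking changed in that arm. It does not test whether EFT changed it. The control condition, Episodic Recent Thinking (ERT), is there to remove change that would have happened anyway, and the protocol gives reasons to expect such change in both arms:

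- Every participant must "express a desire to quit or cut down on their drinking" (Participants).
- Paid breathalyzer screens three times a day start in both arms only after the baseline week (Procedures).
- Regression to the mean is possible, because "participants who indicated adequate patterns of drinking and successfully reported their level of drinking as requested on baseline days will be invited to continue" (Procedures). This is conditional: the SAP does not define the before value, and the protocol sets no threshold or direction for adequate drinking.

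At stake is the trial's only stated hypothesis. The SAP gives no rule for setting the two arms' p-values against each other, so any statement about EFT versus ERT would rest on an unplanned reading.

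**Working it through.** **Which contrast is tested**

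| | Hypothesis (Protocol, Introduction) | Planned test (SAP) |
|---|---|---|
| Quantity | Drinking under EFT minus drinking under control | After minus before, separately in each arm |
| Null hypothesis | No difference between groups | No change in this arm |
| Result | One difference | Two p-values |

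The planned tests do not address the hypothesis. This step needs no numbers.

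**How much it could matter**

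There is no power or sample-size figure to reproduce. The only number is a ceiling: "Up to 200 alcohol-dependent adults will enroll in this study". The following are assumptions:

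- SD of mean drinks/day is 4 before and after, with pre-post correlation r of 0.6 to 0.8.
- Allocation is 1:1 and tests are two-sided at 0.05.
- There are 75 per arm, that is, 150 of the 200 continue past the baseline week.
- The shared fall is s drinks/day, and the true EFT effect is 0 or 1.5 drinks/day on top of it.

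*Paired test.* SD of change = 4 × √(2(1 − r)), which is 3.58 at r = 0.6 and 2.53 at r = 0.8. Power comes from the noncentral t with noncentrality (mean change ÷ SD of change) × √n. At r = 0.6, n = 75 and a 1.5-drink fall, this is 1.5 ÷ 3.58 × √75 = 3.63, giving 94.8% power. If EFT does nothing, both arms are significant with probability 0.948² = 0.90. If EFT adds 1.5 drinks, the EFT arm is almost certain to be significant, so the probability is about 0.95.

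Over a range of shared falls (n = 75, r = 0.6):

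| Shared fall s | Both arms significant: no effect / 1.5-drink effect | Only EFT significant: no effect / 1.5-drink effect |
|---|---|---|
| 0 | 0.3% / 5% | 5% / 90% |
| 0.5 | 5% / 22% | 17% / 78% |
| 1.0 | 44% / 67% | 22% / 33% |
| 1.5 | 90% / 95% | 5% / 5% |
| 2.0 | 99.5% / 99.8% | 0.2% / 0.2% |

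At r = 0.8 the two cases merge sooner: at s = 1.0, both arms are significant in 85% and 92%, and at s = 1.5 in 99.8% and 99.9%.

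*EFT arm read alone, no EFT effect.* With 50 per arm and a shared 1-drink fall, its paired test is significant in 49% (r = 0.6) to 78% (r = 0.8) of trials. With no shared change it keeps its 5% level.

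*Reading 'EFT significant, ERT not' as success.* The SAP does not state this rule. With equal true change and per-arm power p, its false-positive rate is p(1 − p), at most 25%. At 100 per arm and r = 0.6 it is 17%, 1% and 0% for shared falls of 1, 1.5 and 2 drinks.

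*Between-group ANCOVA on the same data.* Residual SD = 4 × √(1 − r²), which is 3.2 at r = 0.6 and 2.4 at r = 0.8. The standard error of the difference at 75 per arm is 3.2 × √(2/75) = 0.52 or 2.4 × √(2/75) = 0.39. For a 1.5-drink effect, power is 81% (r = 0.6) or 97% (r = 0.8). With no effect it rejects in 5%. Neither figure depends on s, because a fall shared by both arms cancels.

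*Change-score t-test as the alternative.* Its variance relative to ANCOVA is 2(1 − r) ÷ (1 − r²) = 2 ÷ (1 + r), which is 1.25 at r = 0.6 and 1.11 at r = 0.8. It therefore needs about 25% or 11% more participants.

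**The case against.** The best defence of the plan is that the SAP's first sentence already provides a between-group t-test. It does not reach the outcomes. Its object is sample characteristics, and the next sentence names alcohol consumption separately and gives it a different test. At most it covers baseline drinking, on which the arms are counterbalanced anyway.

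Three narrower objections stand in part:

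- **The illustration depends on the shared fall.** With none, the paired test in the EFT arm separates the two cases well (5% against 95% significant). The loss is severe only from about 1 to 1.5 drinks upward, and the documents do not say what fall to expect. This limits the size of the problem, not its existence.
- **Regression to the mean cannot be quantified.** A figure would need a screen-out rate, a direction for the drinking criterion and a definition of the before value, none of which is given. It is kept only as a possible mechanism.
- **ANCOVA is not the only remedy.** Any pre-specified between-group contrast of the outcome closes the gap. ANCOVA is preferred for precision.

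**Conclusion.** The concern holds and must be fixed. The SAP's outcome tests are within-group and the hypothesis is between-group. Nothing in either document bridges the two, so following the plan exactly neither supports nor refutes the claim the trial was set up to test. This is a wrong contrast, not a missing detail, and it does not depend on any assumed SD, correlation or arm size.

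The practical size does depend on them. Under the stated assumptions the planned tests range from informative (no shared fall) to nearly uninformative about EFT (shared fall of 1.5 drinks or more), whereas the between-group test keeps its level and power throughout. That level assumes that the counterbalanced allocation behaves like random assignment, which the protocol does not establish.

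**What to change.** Amend the SAP as follows:

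1. Make the primary analysis a comparison of EFT with ERT on mean drinks/day over the 14 intervention days, by ANCOVA with baseline-week mean drinks/day as covariate. Report the adjusted difference with its 95% CI. A two-sample t-test on change scores is acceptable but less precise.
2. Analyse participants in the group to which they were allocated. Include everyone with any intervention-period report, and state how allocated participants with none are handled.
3. Analyse discounting (ln k), alcohol valuation, PANAS and craving in the same way, each with its pre-intervention score as covariate.
4. Keep the paired t-tests, labelled as descriptive.
5. Define the before and after value for each outcome.
6. Say how the allocation was carried out. The protocol says only: "Participants will be counterbalanced to either the active or control group based on alcohol use (e.g., average drinks per day".

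The cost is SAP wording and one model per outcome. The daily reports and assessment sessions needed are already in the protocol, so no participants or visits are added. If ANCOVA is awkward in Prism 7, name another package.
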